## **TITLE**

### **Comparison of Nebulized Sub-dissociative Dose Ketamine at Three Different Dosing Regimens for Treating Acute Pain in the Pediatric ED: A Prospective, Randomized Double-Blind Trial**

## **INTRODUCTION**

Ketamine is a non-competitive N-methyl-D-aspartate (NMDA)/glutamate receptor complex antagonist that decreases pain by diminishing central sensitization, hyperalgesia, and “wind-up” phenomenon at the level of the spinal cord (dorsal ganglion) and central nervous system.

Intravenous ketamine administration in sub-dissociative doses (0.1-0.3 mg/kg) in pre-hospital settings and in the ED results in effective pain relief in patients with acute traumatic and non-traumatic pain, chronic non-cancer and cancer pain, and in patients with opioid-tolerant pain by virtue of providing anti-hyperalgesia, anti-allodynia, and anti-tolerance.

## **BACKGROUND AND SIGNIFICANCE**

In the situation when intravenous access is not readily available or unobtainable, sub-dissociative dose ketamine can be administered via intranasal route (IN). The data supporting intranasal route in pediatric patients is somewhat conflicting with regards to the optimum intranasal dose (range 0.75-1 mg/kg) and frequencies of administration. Hence, another non-invasive route such as nebulization via Breath-Actuated Nebulizer which allows a controlled patient-initiated delivery of analgesics in titratable fashion might be considered in the ED. Administration of fentanyl via BAN for pediatric patients presenting to the ED with acute traumatic musculo-skeletal injuries was found to be safe and effective and comparable to intravenous fentanyl and intravenous morphine

Nebulized administration of ketamine however, has only been studied in the areas of acute postoperative pain management, cancer palliation, and status asthmaticus therapy (ref). To our knowledge, there are no prospective randomized trials that evaluated a role of nebulized SDK role in managing a variety of acute and chronic painful conditions in the ED.

## **STUDY OBJECTIVES**

To compare analgesic efficacy and rates of side effects of sub-dissociative dose ketamine administered via breath-actuated nebulizer at three different doses (0.75mg/kg, 1 mg/kg and 1.5 mg/kg) for pediatric ED patients presenting with acute painful conditions.

## **HYPOTHESIS**

In our study we hypothesize that sub-dissociative-dose ketamine administered as a single agent via breath actuated nebulizer at the dose of 1.5 mg/kg will provide better analgesia at 15 min post-administration with similar rates of side effects in comparison to 0.75 mg/kg and 1 mg/kg for pediatric ED patients presenting to the ED with acute painful conditions. The primary outcome of this trial is the comparative reduction in participant’s pain scores at 15 minutes post medication administration.

## **STUDY DESIGN**

**Subjects:** Pediatric patients aged 7-17 years presenting to the ED with acute painful conditions such as traumatic and non-traumatic abdominal, flank, back, musculoskeletal pain, vaso-occlusive painful crisis of sickle cell disease, and lacerations with a pain score of 5 or more on a standard 11- point (0 to 10) numeric rating scale and requiring sub-dissociative dose ketamine analgesia as determined by the treating

attending physician. Eligible patients will be identified by the primary evaluation of the treating physician, who believes that the patient will benefit from the non-invasive route of Breath Actuated Nebulized (BAN) Sub-Dissociative Dose Ketamine rather than other methods (Intravenous, oral etc.) The treating physician will inform the research team of the potential patient to begin the consenting and enrollment process.

Patients' screening and enrollment will be performed by study investigators and research assistants. All patients will be enrolled at various times of the day when study investigators will be available for patient enrollment and ED pharmacists will be available for medication preparation.

**Eligibility Criteria:** Patients with ages between 7 and 17 presenting to the ED with acute painful conditions such as traumatic and non-traumatic abdominal, flank, back, musculoskeletal pain, vaso-occlusive painful crisis of sickle cell disease, and lacerations with a score of 5 or more on a standard 11- point (0 to 10) numeric rating scale. Patients receiving oral acetaminophen and/or ibuprofen at triage prior to SDK administration will be eligible for the study.

**Exclusion criteria** will include altered mental status, GCS<15, allergy to ketamine, pregnant patients, weight greater than 100 kg, heart rate >180, airway abnormalities (congenital or acquired), absence of parent(s) at the time of consent, closed head injury, seizure disorder, use of opioid analgesics, schizophrenia or bipolar disorder.

**Design:** This is a prospective, randomized, double-blind trial comparing analgesic efficacy and safety of nebulized SDK administered at three different doses to pediatric patients presenting to the ED of Maimonides Medical Center with acute painful conditions. Upon meeting the eligibility criteria, patients will be randomized into one of three study arms based on the dosing of the SDK: 0.75 mg/kg, 1 mg/kg, and 1.5 mg/kg.

**Data Collection Procedures:** Each patient will be approached by a study investigator for acquisition of written informed consent and Health Insurance Portability and Accountability Act authorization after being evaluated by the treating emergency physician and determined to meet study eligibility criteria. When English will not be the participant's primary language, a staff interpreter or licensed telephone interpreter would be used. Baseline pain score will be determined with an 11-point numeric rating scale (0 to 10), described to the patient as "no pain" being 0 and "the worst pain imaginable" being 10. A study investigator will record the patient's body weight and baseline vital signs. The on-duty ED pharmacist will prepare a breath-actuated nebulizer with doses of 0.75 mg/kg, 1 mg/kg, and 1.5 mg/kg according to the predetermined randomization list, which will be created in SPSS (version 24; IBM Corp, Armonk, NY) with block randomization of every 10 participants. The medication will be delivered to the treating nurse in a blinded fashion and will be administered via breath-initiated nebulization for duration of treatment of 10 minutes.

Study investigators will record pain scores, vital signs, and adverse effects at 15, 30, and 60 minutes. In addition, study investigators will record a residual amount of medication (ml) in the nebulizer after the treatment.

If patients reported a pain numeric rating scale score of 5 or greater and requested additional pain relief at 15 minutes mark post-ketamine administration, intravenous morphine at 0.1 mg/kg will be administered as a rescue analgesic.

All data will be recorded on data collection sheets, including patients' sex, demographics, medical history, and vital signs and entered into SPSS (version 24.0; IBM Corp) by the research manager. Development of the randomization list, confirmation of written consent acquisition for all participants, and statistical analyses will be conducted by the research manager and statistician, who would work independent of any data collection.

Patients will be closely monitored for any change in vital signs and for adverse effects during the entire study period (up to 2 h) by study investigators. Common adverse effects that are associated with sub-dissociative dose ketamine are feeling of unreality, dizziness, nausea, vomiting, and sedation.

**Data Analysis:** Data analyses will include frequency distributions, paired t-test to assess a difference in pain scores within each group, and independent-sample t-test to assess differences in pain scores between the 3 groups at the various intervals.

Mixed-model linear regression will be used to compare changes in pain numeric rating scale across time points. This will compensate for participants lost to follow-up and allow all patients' data to be analyzed on an intention-to-treat principle.

For categorical outcomes (eg, complete resolution of pain), a  $X^2$  or Fisher's exact test will be used to compare outcomes at 30 minutes. Percentage differences and 95% confidence intervals between the treatment groups will be calculated for all time points with  $P < .05$  to denote statistical significance. Based on the validation of a verbally administered rating scale of acute pain in the ED and the comparison of verbal and visual pain scales, we will use a primary outcome consisting of a minimal clinically meaningful difference of 1.3 between three groups at the 30-minute pain assessment.

**Expected Outcomes:** The primary outcome will include a comparative reduction in pain scores on numeric rating pain scale (NRS) between recipients of nebulized SDK given at three different doses at 15 minutes after analgesic administration. The secondary outcomes will include a need for rescue analgesia at 15, 30 or 60 minutes and adverse events in each group.

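### No symptom check is planned before dosing and adverse effects are not defined as new or worsened, so presenting symptoms (mainly nausea and dizziness) cannot be separated from drug effects in the dose comparison

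*Combined protocol and SAP*

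**What the plan says.** All of the data collection text is in STUDY DESIGN, Data Collection Procedures. The schedule after dosing is: "Study investigators will record pain scores, vital signs, and adverse effects at 15, 30, and 60 minutes". Before dosing, a pain score is taken on the numeric rating scale, and "A study investigator will record the patient's body weight and baseline vital signs". The data sheet is described in general terms: "All data will be recorded on data collection sheets, including patients' sex, demographics, medical history, and vital signs". The same section adds monitoring for adverse effects throughout the study period, up to 2 hours, and names the common ketamine effects: "feeling of unreality, dizziness, nausea, vomiting, and sedation".

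Under Subjects and Eligibility Criteria, the plan enrols children with "traumatic and non-traumatic abdominal, flank, back, musculoskeletal pain, vaso-occlusive painful crisis of sickle cell disease, and lacerations". The exclusions include altered mental status, GCS below 15 and closed head injury. Nausea, vomiting and dizziness are not exclusions.

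HYPOTHESIS expects the 1.5 mg/kg dose to give better analgesia "with similar rates of side effects in comparison to 0.75 mg/kg and 1 mg/kg". No margin for similarity is stated. Expected Outcomes makes adverse events in each group a secondary outcome. Data Analysis plans chi-square or Fisher tests for categorical outcomes, and percentage differences between groups with 95% confidence intervals. No section says whether a symptom present before dosing counts as an adverse event.

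**The concern.** Pain and vital signs, the other two items recorded at 15, 30 and 60 minutes, each have a baseline value. Adverse effects do not. Several of the listed ketamine effects can also come from the condition that brought the child in, for example nausea with abdominal pain, flank pain or a sickle cell crisis. A child who arrives nauseated and is still nauseated at 15 minutes looks the same on the data sheet as a child made nauseated by the drug. The information cannot be recovered later, and the statistician, who works independently of data collection, has no means of checking how each investigator handled it.

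Randomization balances this background across arms but does not remove it. At stake are the reported tolerability of each dose, which would be overstated, and the ability to detect a dose-related excess. The second matters because similar rates are the stated expectation and no margin is set: a noisier comparison with a ratio nearer 1 is easily read as supporting that expectation.

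**Working it through.** The documents give no sample size, adverse-event rate, similarity margin or prevalence of symptoms at presentation, so there is no planned figure to reproduce. Everything below rests on assumed inputs.

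**Assumed inputs.** n = 60 per arm, equal arms, one pairwise comparison, two-sided 5% level. New-onset rate among children free of the symptom: qL = 10% at a lower dose, qH = 25% at 1.5 mg/kg. A proportion p has the symptom before dosing, is the same in each arm, and still has it afterwards.

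**Formulas.**
- All symptoms counted: rate = p + (1 − p)q.
- Only new symptoms, over all randomized children: rate = (1 − p)q.
- Difference in either case: (1 − p)(qH − qL), because the shared p cancels.
- Standard error of the difference: √{[r1(1 − r1) + r2(1 − r2)]/n}, where r1 and r2 are the two arms' rates.

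**At p = 20%.**
- All counted: 0.20 + 0.80 × 0.10 = 28% and 0.20 + 0.80 × 0.25 = 40%. Difference 12 points, ratio 1.43. SE = √[(0.28 × 0.72 + 0.40 × 0.60)/60] = √(0.4416/60) = 8.6 points.
- New only: 0.80 × 0.10 = 8% and 0.80 × 0.25 = 20%. Difference 12 points, ratio 2.5. SE = √[(0.08 × 0.92 + 0.20 × 0.80)/60] = √(0.2336/60) = 6.2 points.
- The 95% half-widths (1.96 × SE) are 16.8 and 12.2 points, so the interval is about 1.37 times as wide when everything is counted.

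**Across a range of p.** The ratio for new symptoms only is 2.5 in every row.

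| p | All counted | Ratio | SE (points) | Power | New only | SE (points) | Power | Difference, both |
|---|---|---|---|---|---|---|---|---|
| 5% | 14.5% vs 28.75% | 1.98 | 7.4 | 47% | 9.5% vs 23.75% | 6.7 | 56% | 14.25 |
| 10% | 19% vs 32.5% | 1.71 | 7.9 | 39% | 9% vs 22.5% | 6.5 | 53% | 13.5 |
| 20% | 28% vs 40% | 1.43 | 8.6 | 28% | 8% vs 20% | 6.2 | 47% | 12 |
| 30% | 37% vs 47.5% | 1.28 | 9.0 | 21% | 7% vs 17.5% | 5.9 | 42% | 10.5 |
| 40% | 46% vs 55% | 1.20 | 9.1 | 16% | 6% vs 15% | 5.5 | 36% | 9 |

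**The denominator.** Among children free of the symptom at baseline, the difference is 25 − 10 = 15 points. The fall from 15 to 12 points at p = 20% is the factor (1 − p), and it appears only against that subgroup. Over all randomized children the expected difference is 12 points whether or not pre-existing symptoms are counted.

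**Sensitivity to the rates.** With new-onset rates of 20% and 40%, p = 20% and 60 per arm, counting everything gives 36% vs 52% (ratio 1.44, power 42%). New symptoms only give 16% vs 32% (ratio 2.0, power 54%). The difference is 16 points both ways. The pattern is the same, with a smaller loss of power.

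**The case against.** The strongest reply is that the plan never says presenting symptoms are counted. A reader might infer from the recording schedule that a child who arrives nauseated becomes an adverse event for the assigned dose. The documents do not support that as a rule. They describe the effects as those associated with ketamine, the treating physician evaluates each child before enrolment, and an investigator could reasonably leave out a known presenting complaint. The data-sheet list is also not exhaustive. This part of the objection stands: the counting is undefined. It does not remove the concern, because the alternative is unrecorded judgement made child by child.

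A reader might also infer that the planned dose difference is pulled toward zero. That is not so for the percentage difference over all randomized children, whose expected value is unchanged. What suffers is the ratio, which the plan does not say it will report, together with the precision of the difference and the power of the planned tests.

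Three further limits are fair. Prevalence at presentation is unknown, and the eligible conditions include lacerations and musculoskeletal pain, so 5% to 10% is as admissible an assumption as 20% to 40%. The exclusions for altered mental status and GCS below 15 limit pre-existing unreality and sedation. Vomiting before arrival does not count again unless it recurs, so nausea and dizziness are the main exposure. Finally, adverse events are a secondary outcome, assessed under blinding.

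**Conclusion.** The gap is real and worth closing. No symptom record precedes dosing and no new-or-worsened definition exists, so background symptoms cannot be separated from drug effects at any of the three time points. The plan does not state that such symptoms count as ketamine effects, and it should not be read as if it did.

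If they are counted, the per-arm rates are inflated, the ratio between doses moves toward 1, and the confidence interval for the percentage difference widens. With the assumed 10% and 25% new-onset rates and 60 per arm, the standard error rises by about 11% at 5% prevalence (7.4 against 6.7 points), by about 21% at 10% prevalence (7.9 against 6.5) and by about 37% at 20% prevalence (8.6 against 6.2). The expected percentage difference over all randomized children does not change. These sizes rest wholly on assumed rates, prevalence, persistence and arm size. Because similar rates are hypothesized without a margin, the loss of precision works in favour of the trial's own expectation.

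**What to change.** In Data Collection Procedures, have the investigator ask the five symptoms the protocol already names, graded none, mild, moderate or severe, immediately before nebulization and again at 15, 30 and 60 minutes. In Expected Outcomes, define the side-effect outcome as a symptom that is new or at least one grade worse than before dosing. In Data Analysis, state that all randomized children form the denominator. The worsening rule lets children who arrive with symptoms contribute information; the calculation above does not model that gain.

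The cost is one more column on the data sheet, one sentence of definition, and about a minute per child, carried out by the investigator who already records baseline weight and vital signs. Treatment does not change.

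### No severity scale is specified for adverse effects, so similar rates at 1.5 mg/kg would not show whether the effects are more intense

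*Combined protocol and SAP*

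**What the plan says.** All references are to the combined protocol and SAP.

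- **Study Objectives.** The aim is "To compare analgesic efficacy and rates of side effects of sub-dissociative dose ketamine" at three doses. Harm is framed as a rate.
- **Hypothesis.** The highest dose is expected to give better analgesia at 15 minutes "with similar rates of side effects in comparison to 0.75 mg/kg and 1 mg/kg". No margin for similarity is given.
- **Study Design, Data Collection Procedures.** "Study investigators will record pain scores, vital signs, and adverse effects at 15, 30, and 60 minutes". Monitoring for adverse effects continues for up to 2 hours. The effects described as common are "feeling of unreality, dizziness, nausea, vomiting, and sedation". Pain has an anchored 0 to 10 scale; adverse effects have no scale. On the form itself the text says "All data will be recorded on data collection sheets, including patients' sex, demographics, medical history, and vital signs". The form is not reproduced.
- **Study Design, Data Analysis.** Categorical outcomes are compared at 30 minutes by chi-square or Fisher's exact test, and percentage differences with 95% confidence intervals are calculated for all time points. Adverse events are not mentioned by name here, and no ordinal or graded analysis of them is described.
- **Study Design, Expected Outcomes.** "The secondary outcomes will include a need for rescue analgesia at 15, 30 or 60 minutes and adverse events in each group".

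**The concern.** The plan measures how strong the benefit is but, as written, only whether harm occurred. That matters more than usual in this trial for two reasons. First, the arms differ only in dose, over a twofold range (1.5 / 0.75 = 2). Second, the plan itself calls the listed effects common. When most children in every arm may have some effect, a higher dose can make the effects stronger without making them much more frequent. Unreality, dizziness, nausea and sedation all vary in intensity.

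The conclusion the trial hopes to reach has two halves: better analgesia at 1.5 mg/kg, and side effects no worse than at the lower doses. If the second half rests on rates alone, it may be read as a statement about tolerability that the data cannot support. Intensity that is not captured at the bedside cannot be reconstructed afterwards.

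**Working it through.** **1. What can be reproduced.** Nothing. The documents give no sample size, allocation ratio, power, adverse-event rate, similarity margin or severity scale. The point rests on reading the text; the numbers below are illustrations on assumed inputs.

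**2. Does the gap depend on pooling?** The plan does not say whether effects are pooled or listed by type.

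- Pooled into one any-effect count: every effect of any intensity counts once.
- Listed by type: dizziness and sedation are separate rows, but within the sedation row a drowsy child and a markedly sedated child each count once.

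Intensity within a type is lost either way. Only the first layout also merges different effects.

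**3. How large a difference could go unseen?** Let *a* be the any-effect rate, assumed equal in two arms, and let *s0* and *s1* be the shares of affected children whose effect is moderate or severe.

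- Difference in any-effect rate = *a* − *a* = 0.
- Difference in moderate-or-severe rate = *a* × (*s1* − *s0*).
- With *a* = 60%, *s0* = 10%, *s1* = 50%: 6% versus 30%, a difference of 0.60 × 0.40 = 24 points.
- Smallest case in the range examined: 0.40 × (0.30 − 0.10) = 8 points. Largest: 0.80 × (0.50 − 0.10) = 32 points.

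Because *a* is set equal, a larger trial does not help the any-effect comparison.

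**4. What would grading recover?** Exact power of Fisher's test, two-sided 0.05, with *n* per arm:

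power = Σᵢ Σⱼ Bin(i; n, p₀) × Bin(j; n, p₁) × 1[Fisher p(i, j) ≤ 0.05]

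| Comparison (assumed rates) | n per arm | Probability of p ≤ 0.05 |
|---|---|---|
| Any effect, 70% v 70% | 40 | 0.028 |
| Moderate or severe, 10% v 35% | 20 | 0.361 |
| Moderate or severe, 10% v 35% | 40 | 0.717 |
| Moderate or severe, 10% v 35% | 60 | 0.887 |
| Moderate or severe, 10% v 20% | 40 | 0.162 |

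The first row is simply the test's type I error: there is no difference to find. The last row shows that a smaller rise in severity would usually be missed even with grading.

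**5. Precision in the weaker case.** For 10% v 20% at 40 per arm, the approximate 95% half-width is 1.96 × √[(0.10 × 0.90 + 0.20 × 0.80) / 40] = 1.96 × √(0.25 / 40) = 0.155. A 10-point difference would carry an interval of about ±15 points. That is a reason to report the interval and not only a p-value.

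**The case against.** **The plan is silent; it does not rule severity out.** A reader might infer that side effects will be recorded without severity. The documents do not support that. The form is not shown, and the list of its contents is introduced as a partial one: it omits even pain scores and adverse effects, which the same section says are recorded. This objection stands. What can be said is that no scale and no graded analysis are specified, so a grade that happened to be written down would have no agreed definition and no planned use.

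**Different effects need not be merged.** A reader might also infer that mild dizziness would count the same as marked sedation. That is true only of a pooled any-effect count, which the plan does not prescribe; "adverse events in each group" fits a table by type equally well. This objection also stands. The narrower point, that mild and marked forms of one effect count alike, does not depend on the layout.

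**The list of effects is not an instrument.** It describes what is commonly seen with the drug. Correct: the recording sentence and the hypothesis carry the point, and the list shows only that the plan expects these effects to be common.

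**The illustration is constructed.** It sets any-effect rates equal while severity rises sharply. If severity rises with dose, incidence may rise too, and a plain count would then show something. Agreed: the example shows what is possible, not what is likely.

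**Some information beyond presence or absence is planned.** Vital signs are taken at each assessment, and children are monitored for up to 2 hours. It would therefore be too strong to say that important physiological effects are invisible. Vital signs do not, however, grade unreality, dizziness or nausea.

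**Rates match the stated objective, and adverse events are secondary.** Also true. Nothing here is a contradiction, and the primary pain comparison is untouched.

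**Conclusion.** The point holds as a gap in specification. No severity scale is defined, the safety half of the hypothesis is worded as rates, and the analyses that fit adverse events compare proportions. A finding of similar rates at 1.5 mg/kg would therefore leave open whether the effects are more intense than at the lower doses.

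Its size is unknown. On assumed any-effect rates of 40% to 80%, equal between arms, the unseen difference in moderate-or-severe effects ranges from 8 to 32 percentage points. Those figures rest wholly on the assumed rates and shares. The power figures rest as well on an assumed 40 per arm (20 and 60 as alternatives).

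The documents do not support the inference that the trial will conceal greater harm at the highest dose, or that the investigators will fail to note severity. They support only the statement that the plan does not secure the information. This is a worthwhile, inexpensive improvement to a secondary outcome, not an error that threatens the primary result.

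**What to change.** **Data Collection Procedures.** Record each listed effect at 15, 30 and 60 minutes with a short grade: none, mild, moderate or severe. Give each grade a one-line anchor suited to children aged 7 to 17, and have the blinded investigator assign it. If the form already holds such a grade, describe it in the protocol.

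**Data Analysis and Expected Outcomes.** State that adverse effects will be reported by type and by child, with each child counted once at the worst grade. For 1.5 mg/kg versus each lower dose, give the proportion with any effect and the proportion with a moderate or severe effect, each with the difference and its 95% confidence interval. Base any statement that side effects are similar on both.

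**Cost.** One extra field per effect on a form already completed at the bedside, and one more table. No added patients, assessments or procedures, and no change to treatment. There are two downsides. Grading is partly subjective, which anchors and blinding limit but do not remove. The graded comparison may also have low power, so a non-significant result must not be read as evidence of similar severity; the intervals should carry the interpretation.

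### No primary between-dose analysis is named, and neither candidate adjusts for the baseline pain score that every patient has

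*Combined protocol and SAP*

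**What the plan says.** All references are to the combined protocol and SAP.

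- **Data Analysis, first method:** "independent-sample t-test to assess differences in pain scores between the 3 groups", at each assessment time. No covariate is mentioned. The paired t-test listed beside it works within a group and compares no doses.
- **Data Analysis, second method:** "Mixed-model linear regression will be used to compare changes in pain numeric rating scale across time points". The section gives no fixed effects, no dose-by-time contrast and no rule for handling baseline. It credits this model with coping with loss to follow-up and with keeping all patients in an intention-to-treat analysis.
- **Primary outcome:** the Hypothesis section defines it as a comparative reduction in "pain scores at 15 minutes post medication administration". Expected Outcomes repeats this for ketamine "given at three different doses at 15 minutes after analgesic administration". Neither sentence attaches a test. Data Analysis, however, ties the primary outcome to a "minimal clinically meaningful difference of 1.3 between three groups at the 30-minute pain assessment".
- **Baseline:** Data Collection Procedures has the pain score taken at baseline on the 0 to 10 scale. The Subjects paragraph admits patients "with a pain score of 5 or more on a standard 11- point (0 to 10) numeric rating scale".

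**The concern.** Two analyses could each supply the main between-dose result, and the plan does not say which one counts. One is worded on scores and the other on changes, while the primary outcome is a reduction. With complete data, a score contrast and a change contrast differ by exactly the chance difference in mean baseline between the arms. The two can therefore disagree at the primary time point, and the choice could be made after the results are known.

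As written, the t-test on scores ignores a baseline measurement that is likely to predict the outcome. An unadjusted mixed-model contrast from baseline would amount to a change-score comparison, which uses baseline but not necessarily efficiently. Adjustment would narrow the interval around each dose difference without adding a patient.

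**Working it through.** The plan states no sample size, power, SD or correlation, so there is no figure of its own to reproduce.

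**Inputs**

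- From the documents: three arms; baseline integers 5 to 10; follow-up scale 0 to 10; a difference of 1.3 points.
- Assumed: correlation *r* between baseline and 15-minute score of 0.2, 0.4 and 0.6; total *N* of 60 to 120 in equal arms; *k* = baseline SD / 15-minute SD of 0.6 to 0.8. Values of *k* below 1 are plausible because entry restricts the baseline: its SD is sqrt(35/12) = 1.71 if scores are uniform on 5 to 10, and at most 2.5.

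**1. Adjustment against a t-test on the score**

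The variance ratio is 1 − r², the CI width ratio is its square root, and the equivalent extra patients are 1/(1 − r²) − 1.

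| r | Variance ratio | CI width ratio | Equivalent extra patients |
|---|---|---|---|
| 0.2 | 0.96 | 0.98 | 4% |
| 0.4 | 0.84 | 0.92 | 19% |
| 0.6 | 0.64 | 0.80 | 56% |

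**2. Cost of estimating the slope**

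With three arms the variance is multiplied by 1 + 1/(N − 5), which is 1.018 at N = 60 and 1.009 at N = 120.

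- Net saving at N = 60: from 1 − 0.96 × 1.018 = 2.3% to 1 − 0.64 × 1.018 = 34.8%.
- Net saving at N = 120: 3.2% to 35.4%.
- Break-even is at r² = 1/(N − 4), so r = 0.13 at N = 60 and 0.09 at N = 120.

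**3. Adjustment against a change score**

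The variance ratio is (1 − r²)/(1 + k² − 2rk), before the slope cost.

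| r | k = 0.6 | k = 0.8 |
|---|---|---|
| 0.2 | 0.96/1.12 = 0.86 | 0.96/1.32 = 0.73 |
| 0.4 | 0.84/0.88 = 0.95 | 0.84/1.00 = 0.84 |
| 0.6 | 0.64/0.64 = 1.00 | 0.64/0.68 = 0.94 |

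The saving is thus about 0% to 27%.

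**4. Simulation check**

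Twenty thousand trials were simulated with an assumed 30 per arm and baseline uniform on 5 to 10. Adjusted/score ratios were about 0.97, 0.85 and 0.65 at r = 0.2, 0.4 and 0.6. Adjusted/change ratios were about 0.87, 0.96 and 1.01 at k = 0.6, and about 0.74, 0.85 and 0.95 at k = 0.8. These include the slope cost and agree with the formulas.

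**5. How far the two candidates can disagree**

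The score and change contrasts differ by the baseline mean difference, whose 95% range is ±1.96 × SD × sqrt(2/n). With a uniform baseline this is ±1.06 points at an assumed 20 per arm and ±0.75 at 40 per arm. Those are 81% and 58% of the 1.3-point difference.

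**6. In patients and power**

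Assume a 15-minute SD of 2.5, two-sided alpha of 0.05, 80% power and a pairwise difference of 1.3. A score t-test needs 59 per arm. The adjusted analysis needs 56, 49 or 38 at r = 0.2, 0.4 or 0.6. With 59 per arm, power rises from 0.81 to 0.82, 0.87 or 0.94.

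**The case against.** The strongest reply is that the primary outcome is a reduction. If the t-test is run on change, baseline already enters by subtraction. The mixed model may also use baseline as a time point or a covariate. The fair comparator would then be the better of score and change. On the same assumptions, adjustment saves 4% against that comparator at r = 0.2, about 5% (k = 0.6) or 16% (k = 0.8) at r = 0.4, and 0% or 6% at r = 0.6. The overall range is 0% to 16%, before the slope cost. Entry at 5 or more probably lowers the correlation as well, so the low end deserves weight.

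Much of this stands as a limit on the size. The t-tests are valid, the loss is demonstrable only for them, and for the mixed model the defect is silence. It does not remove the point. The t-test is worded on pain scores, so baseline is unused in it as written. Nobody can know beforehand which of score and change will be the more precise. Apart from about one degree of freedom, the adjusted analysis is at least as precise as either. It also gives the same dose contrast for score and for change, which removes the ambiguity. The intention-to-treat remark hints that the mixed model may govern, but it does not designate it.

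**Conclusion.** The concern holds. It is a matter of efficiency and pre-specification and should be corrected, but the trial is not biased or invalid without the change. The textual gap is certain: no primary between-dose analysis is designated and no baseline covariate is stated. The gain is not certain, because every SD, correlation and sample size used here is assumed. Net of the slope cost, it is about 2% to 35% of variance against the score t-test as worded. It is smaller, and possibly nil, against a change score. The missing designation matters whatever the correlation turns out to be.

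**What to change.** First reconcile the 15-minute primary time point in Hypothesis and Expected Outcomes with the 30-minute statement in Data Analysis. Then name one primary between-dose analysis at 15 minutes, either:

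- **(a)** ANCOVA of the 15-minute score on dose group, with the baseline score as covariate; or
- **(b)** the planned mixed model with post-baseline scores as outcome and terms for dose, time, dose-by-time, baseline and baseline-by-time, reading off the dose contrasts at 15 minutes.

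Report adjusted dose differences with 95% confidence intervals. Make the t-tests supportive and keep within-arm change as description. The same text should say which dose contrast or contrasts carry the primary conclusion, since the hypothesis sets the highest dose against each of the other two and naming a model does not settle that.

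The cost is SAP wording and one degree of freedom for the baseline slope in the ANCOVA. No new data are needed.
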